3.1.2 Pharmacology

Non-clinical pharmacology studies have demonstrated ATX-101's efficacy in inhibiting the growth of cancer cells in a broad range of cancer cell lines in vitro, as well as in different in vivo models. The APIM consensus sequence is validated as a functional PCNA-binding motif that occurs in numerous proteins involved in DNA repair and damage tolerance. ATX-101 was shown to directly interact with PCNA and to be able to impair APIM-PCNA interaction in live cells. For example, peptides containing the APIM-motif such as ATX-101 inhibit the interaction between PCNA and the essential translesion synthesis DNA polymerase POL ζ . ATX-101 was shown to reduce the function of POL ζ in TLS. Thus, ATX-101 impairs the cells' ability to tolerate DNA lesions and thereby contributes to anti-cancer activity. Additionally, ATX-101 displayed anti-mutagenesis properties by attenuating spontaneous and ultraviolet (UV)-induced mutagenesis in E. Coli MG1655 cells.

In vitro, it has been shown that ATX-101 is able to induce apoptosis of cancer cell lines in a cell cycle-independent manner. From a panel of 44 cancer cell lines, originating from a range of organs, ATX-101 was shown to have a dose-dependent growth inhibitory effect as a single

agent. ATX-101 was also shown to potentiate the growth inhibitory effect of different chemotherapeutic and targeted agents in these cell lines.

In vivo, the efficacy of ATX-101 in potentiating the effect of chemotherapeutic and targeted agents to reduce tumor growth was demonstrated using tweleve different models. Administered in combination therapy, ATX-101 did not increase the toxicity observed above that of the anticancer agents alone.

3.1.3 Plasma protein binding

Not available

3.1.4 Metabolism

Not available

3.1.5 Enzyme Interactions

Not available

3.1.6 Toxicology

The toxicity of ATX-101 was assessed in the rat and in the dog. Preliminary studies were undertaken to compare several dose levels of ATX-101 after a single IV administration or over a 4-cycle treatment period, ranging from 12 to 80 mg/kg/dose in the rat and up to 25 mg/kg/dose in the dog, in order to set the dose range to be evaluated in the 6-cycle (35 days) repeated-dose studies. In the main rat study, ATX-101 treatment induced body weight losses for dose levels of 30 mg/kg and above, and the maximum tolerated dose (MTD) was considered to be 30 mg/kg (180 mg/m2) over 6 weekly administrations. In the main dog study, the MTD was considered to be at least 22.5 mg/kg (450 mg/m2) over 6 weekly IV administrations. Results in the rat, being the most sensitive species, and the corresponding MTD of 30 mg/kg were used for the determination of the phase 1 starting dose in human patients.

GLP-compliant safety pharmacology studies demonstrated that IV infusion of ATX-101 does not lead to any effect on the central and peripheral nervous systems of rats at dose levels up to 30 mg/kg. In the cardiovascular and respiratory study performed in dogs, increased heart rate was observed associated with higher arterial blood pressure, reduced pulse and respiratory frequency. However, all these effects were transient and returned to normal within approximately 1 hour post-end of infusion without any medication. These effects are currently attributed to histamine release induction by the peptide.

ATX-101 elicited an infusion reaction in the rat and in the dog, characterized by the appearance of edema localized mainly to the head during the treatment, as well as, in the dog, retching, emesis, and excessive struggling. This reaction was moderate and transient, resolving spontaneously within a few hours, without any medication. Symptoms of these reactions corresponded to a transient peak of histamine plasma levels in dogs.

In the rat studies, one animal in each of the ATX-101 groups at 30 (study WIL-63506), 55 or 80 mg/kg (study WIL-63513) died just after the third infusion, and showed dark red areas in the lungs at necropsy. The cause of death for these three animals was undetermined. These macroscopic observations were reported in three additional animals that survived to the scheduled necropsy, including one untreated recovery animal. According to historical data from WIL Research (contract research organization in charge of these studies), this effect is seen in 1% of untreated rats. After re-analysis of the rat data by an independent anatomic pathologist, it was concluded that the death of these three animals could not clearly be attributed to ATX-101. No gender effect was evident in rats or in dogs in these studies.

3.1.7 Cardiovascular Effects

Not available

3.1.8 Genotoxicity

Not available

3.1.9 Carcinogenicity

None performed.

3.1.10 Developmental and Reproductive Toxicity

None performed.

3.2 Clinical Data

ATX-101 is currently being evaluated in the first in human study (ATX101-01 and -02), a phase 1 dose escalation study in solid tumors. In this study patients with solid tumors who have no further treatment options are enrolled at three active sites in Australia in a 3+3 study design. In the ATX-101-01 study ATX-101 is infused weekly over 6 weeks whereas the ATX-101-02 is a long term follow-up study in which ATX-101 is infused continuously with the same weekly regimen in patients who have not progressed after the 6 weeks of initial treatment. The ATX-101 dose used in this study ranged from 20 mg/m² IV once weekly to 60 mg/m² IV once weekly. Although no MTD was reached, after review of the available safety data, the RP2D was determined to be 60 mg/m2 IV weekly, with no plans for dose-escalate further.

Of the 21 patients enrolled in this study, 3 patients had sarcoma: one with uterine LMS, one with gastrointestinal stromal tumor (GIST) and 1 with undifferentiated pleomorphic sarcoma (UPS). While there were no responses according to RECIST, multiple patients experienced prolonged stabilization of disease, including the patient with uterine LMS who remained stable for more than 16 months of treatment.

As of October 31st, 2020, there have been no deaths with in 30 days of treatment with ATX-101. In general treatment has been well tolerated with patients discontinuing treatment with ATX-101 as a consequence of disease progression rather than toxicity. No ATX-101 related grade 3 or higher adverse events (AEs) or serious adverse events (SAEs) have been reported during the entire study duration. No dose limiting toxicity (DLT) has been observed. The most frequently observed ATX-101 related AEs were infusion related reaction. Grade 1 infusion reactions were reported in 13/21 patients and grade 2 infusion reactions were reported in 14/21 patients over the entire duration in all patients. Reported infusion reactions included itchiness, redness, urticaria, fever, rash, swelling, flushing, hives and confusion. Infusion reactions occurred during the first but also during later infusions and resolved completely after ATX-101 infusion interruption and/or treatment with corticosteroids and/or antihistamines. In the majority of patients, the infusion of ATX-101was safely restarted and treatment was completed. So far, there is no evidence for a dose relationship of infusion reactions. The mandatory premedications consisted of dexamethasone, histamine 1 and 2 receptor antagonists, acetaminophen and montelukast. Besides, infusion reactions, ATX-101 related AEs reported at least twice during the entire study duration were fatigue (6 times), diarrhea (3 times) and dysgeusia (2 times). All of these were grade 1 in severity with the exception of 2x fatigue which were grade 2. The table below reports all the adverse events observed in these 21 patients until October 31st, 2020.

Event (Preferred Term)	Cohort 1 20 mg/m ² (n=8)	Cohort 2 30 mg/m ² (n=3)	Cohort 3 45 mg/m ² (n=4)	Cohort 4 60 mg/m ² (n=6)
Grade 1: mild	4 (50%)	3 (100%)	4 (100%)	4 (66.7%)
Grade 2: moderate	2 (25%)	1 (33.3%)	3 (75%)	5 (83.3%)
Grade 3: severe	0	0	0	0
Grade 4: life threatening	0	0	0	0

Treatment related treatment emergent adverse events observed in study AM ATX101-01 (31 October 2020) – Number (%) of patients experiencing an adverse event, by dose level.

Treatment related treatment emergent adverse events observed at least twice in study AM ATX101-
01 (31 October 2020) – Total number of events experienced by all patients on the study

Event (Preferred Term)	Grade 1	Grade 2	Grade 3	Grade 4
Infusion related reaction	13	14	0	0
Fatigue	4	2	0	0
Infusion site conditions*	3	2	0	0
Dysgeusia	3	0	0	0
Diarrhea	2	0	0	0

* Includes local infusion site -erythema; -extravasation; -pruritus; -urticaria; -reaction.

4. STUDY DESIGN

4.1 General Design

[figure not shown]
This is a phase II, single-arm, open-label, Simon 2-stage study evaluating the efficacy of ATX-101 in patients with unresectable or metastatic LMS or dedifferentiated LPS who have received treatment with at least one prior systemic therapy.

Because clinical data with ATX-101 is limited, a safety lead-in will be conducted among the first 10 patients enrolled and treated on the study. The safety lead-in is described in Section 4.2.

The study will be conducted at Columbia University Irving Medical Center. All subjects will be treated with the same agent and dose, ATX-101, at 60 mg/m² IV weekly in continuous 21 day cycles. Patients will receive treatment at the discretion of the principal investigator until disease progression, unacceptable toxicity or adverse event(s) or withdrawal of consent.

The primary endpoint is the progression free rate at 12 weeks (PFR₁₂). Secondary endpoints include overall survival, progression free survival, overall response rate and safety profile.

For further details on the statistical design, see Section 9.

4.2 Safety Lead-In

Recognizing the limited clinical experience with ATX-101, we will perform a safety lead-in among the first 10 patients enrolled and treated on the study to confirm the safety and tolerability of the proposed dose and schedule. The safety lead-in will apply to the first 10 patients treated for two cycles (6 weeks). These patients will undergo safety assessments as specified in the study calendar.

The study will not proceed to further accrual until these 10 patients have completed two cycles or 6 weeks of study treatment; however, patients who end study treatment during this period for reasons other than toxicity, i.e., disease progression, will not be replaced. After 10 patients complete 2 cycles of treatment, the study investigators will review the safety data. If 3 or more patients in the safety lead-in population experience DLTs as defined below, the study team will consider terminating the study or amending the study to evaluate an alternative dose and schedule. In addition, if 2 or more events of grade 4 infusion related reaction occur, the study team will also consider terminating the study. Formal documentation of the study team's review of toxicity data from the safety lead-in will be provided to the IRB and FDA prior to resuming accrual.

The following definitions of dose-limiting toxicity (DLT) apply to the safety lead-in. DLTs are defined as the following toxicities which are attributed as at least possibly related to the study drug and not to disease, and which occur (or first become evident) during a prespecified timeframe. For the purposes of the safety lead-in, this timeframe is the first two cycles of treatment.

- Any grade ≥3 non-hematologic toxicity, except grade ≥3 fatigue, nausea, or vomiting which must persist >5 days despite maximal supportive care to be considered dose limiting. This includes any grade 3 or 4 infusion-related reaction.
- 2. Any grade \geq 4 hematologic toxicity lasting >14 days, except grade 4 lymphopenia, which is not considered a DLT.
- 3. Grade \geq 3 neutropenia with fever
- 4. Grade \geq 3 thrombocytopenia with clinically significant bleeding.
- 5. Any laboratory abnormality not otherwise addressed above which is both associated with clinical sequelae and which fails to resolve to grade ≤1 within 5 days of occurrence, or any laboratory criteria meeting Hey's law for liver toxicity.

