11. STUDY CALENDAR

CBC w/differential (1,3)*	Х	Х	Х	Х	Х		Х		Х
Comprehensive metabolic panel (1,3,4)*	Х	Х	Х	Х	Х		Х		Х
Serum or urine pregnancy test (1, 3)	Х								Х
Urinalysis (1, 3)	Х						Х		Х
CT or MRI of chest, abdomen, pelvis (2)	Х						Х		Х
Tumor biopsy for correlative studies (5)	Х				X				
Follow-up telephone contact (6)	llow-up telephone contact (6)				Х				
*Clinical/laboratory safety assessm	ents must	be con	nple	ted w	ithin 24	4 hours	prior to	treatmen	t.

(1) Screening procedures must be completed within 21 days of initiating study treatment, with the exception of the serum or urine pregnancy test, which must be completed within 7 days of initiating study treatment. Protocol-specified screening procedures that are performed as part of standard of care and are within the specified timeframes may be used for screening purposes.

(2) Baseline imaging can include either (a) CT, spiral CT or MRI, or (b) FDG-PET with diagnostic CT performed with IV and oral contrast and CT acquired with 5 mm or less slice thickness. Imaging studies used for baseline tumor measurements must be performed within 21 days of initiating study treatment. Imaging studies are performed every 2 cycles (6 weeks, 42 days) for the first 36 weeks of study treatment, and then every 3 cycles (9 weeks, 63 days) thereafter. Imaging studies may be performed +/- 5 days from the required date. In the event of dose delays/holds, imaging studies should still be obtained at the scheduled timepoints as measured from cycle 1 day 1, without delays to account for dose delays/holds. Confirmatory scans must be obtained at least 4 weeks after the documentation of an objective response. It is acceptable to perform confirmatory assessments at the next appointed evaluation per protocol. Response assessment should include assessment of all sites of disease and use the same imaging method as used at baseline whenever possible.

(3) All laboratory studies may be performed +/- 3 days from the required date. Local laboratory testing is permitted, except for the serum/urine pregnancy test.

(4) Comprehensive metabolic panel includes albumin, alkaline phosphatase, total bilirubin, bicarbonate, blood urea nitrogen, calcium, chloride, creatinine, glucose, potassium, total protein, AST, ALT and sodium.

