15. STATISTICAL PLAN

15.1 Primary Endpoint

The primary endpoint is the progression free rate at 12 weeks (PFR₁₂). This corresponds to the number of patients who are alive and without evidence of disease progression at 12 weeks out of all evaluable patients.

Two recent randomized phase 3 studies evaluated novel agents (trabectedin, eribulin) in a population of patients with LPS and LMS. In both studies, the cytotoxic agent dacarbazine was used as the active comparator/control arm. Dacarbazine is a chemotherapy agent often used for later-line treatment of soft tissue sarcoma, including LPS and LMS.

In the randomized study of trabectedin versus dacarbazine in patients with LPS and LMS (n=518), median PFS was 4.2 months versus 1.5 months, and the progression-free rate at 3 months (12 weeks) was 56% versus 34%, respectively[1]. In a subset analysis, outcomes were similar in LPS and LMS. Similarly, in the randomized study of eribulin versus dacarbazine (n=452), the median PFS was 2.6 months versus 2.6 months, and the progression-free rate at 3 months (12 weeks) was 33% versus 29%.[2]

Based upon the results of these studies, a $PFR_{12} \le 30\%$ would be considered inactive and unworthy of further study, whereas a $PFR_{12} \ge 55\%$ would suggest clinically meaningful activity, worthy of further evaluation in subsequent studies.

A Simon optimal 2-stage design is used. The study will enroll 10 patients with LMS and LPS in the first stage. If 4 or more patients meet the PFR_{12} endpoint in the first stage (4/10), the study will proceed to the second stage, enrolling an additional 24 patients for a total sample size of 34 patients. If 15 or more total patients meet the PFR_{12} endpoint in the overall study population (15/34), the agent will be considered promising and worthy of further study.

An interim analysis will be performed after the first stage is completed. In the event that the study meets the stage 1 endpoint, but all patients who meet the PFR_{12} endpoint are of the same histology (either LMS or LPS), then the study will proceed to full accrual in that respective histology only. In this event, no further patients will be enrolled from the histology in which no patients met the PFR_{12} endpoint during stage 1.

This design provides 85% power and type 1 error (1-sided) of 0.05 to evaluate for an improvement in PFR_{12} from $\leq 30\%$ to $\geq 55\%$.

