15.2 Size/Accrual Rate

The sample size is 34 patients. The planned accrual rate is 2-3 patients per month. Therefore, accrual is expected to be complete in no more than 17 months. Assuming patients continue treatment for up to 1 year (12 months) and allowing 6 months for quality assurance, the anticipated duration of the study is approximately 35 months.

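### Could accrual resume after the 6-week safety hold, before the 12-week stage-1 result is known?

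*Combined protocol and SAP*

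**What the plan says.** Section 4.2 (Safety Lead-In) sets a hold after the tenth patient: "The study will not proceed to further accrual until these 10 patients have completed two cycles or 6 weeks of study treatment". The investigators then review the safety data, and formal documentation of that review "will be provided to the IRB and FDA prior to resuming accrual".

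Section 15.1 (Primary Endpoint) uses 10 patients as stage 1. If at least 4 of them are alive and progression-free at 12 weeks, "the study will proceed to the second stage, enrolling an additional 24 patients for a total sample size of 34 patients". On timing it says: "An interim analysis will be performed after the first stage is completed". If every stage-1 success has the same histology, "no further patients will be enrolled from the histology in which no patients met" the endpoint.

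Section 11 (Study Calendar, note 2) fixes the scans: "Imaging studies are performed every 2 cycles (6 weeks, 42 days) for the first 36 weeks of study treatment". The 12-week endpoint is therefore read at the second on-treatment scan.

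Section 15.2 (Size/Accrual Rate) says "The planned accrual rate is 2-3 patients per month", and that "accrual is expected to be complete in no more than 17 months".

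**The concern.** The same 10 patients run on two clocks. The safety clock in section 4.2 can expire at week 6 of the tenth patient. The efficacy clock in section 15.1 runs to week 12. Section 4.2 is the only place with an explicit hold and resumption for these patients, and it is silent on efficacy. Section 15.1 does not say in so many words that accrual is suspended while the 12-week data mature. The 17 months in section 15.2 equals 34 divided by 2, with no pause.

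If staff acted on section 4.2 alone, some stage-2 patients would be treated before the futility rule had been applied. A Simon optimal design is chosen to minimise the expected number treated when the drug is inactive, and that number would rise. The single-histology rule would also come too late for patients already enrolled in the histology that closes.

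**Working it through.** **Inputs.** From section 15.1: continue with at least 4/10, success with at least 15/34, null rate 0.30, alternative 0.55. From section 15.2: 2 to 3 patients per month (2.5 is used as a midpoint). From sections 4.2 and 11: 6-week hold and 6-week scans. Assumed: even accrual and a month of 30.44 days, so 6 weeks = 42/30.44 = 1.38 months and 12 weeks = 2.76 months.

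**1. The plan's own design figures.** The probability of declaring success at rate p is the sum over x = 4 to 10 of P(X₁ = x; 10, p) × P(X₂ ≥ 15 − x; 24, p).
- At p = 0.30: 0.0456, within the stated 0.05.
- At p = 0.55: 0.853, matching the stated 85%.
- P(stop at stage 1 | 0.30) = P(X ≤ 3; 10, 0.30) = 0.650.
- Expected N at 0.30 = 10 + 24 × (1 − 0.650) = 18.4.

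A search over designs confirms that this is the optimal design for these targets.

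**2. Patients exposed if section 4.2 were the only gate.** Gap = rate × 1.38. Expected N = 18.41 + 0.6496 × gap.

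| Rate per month | Gap patients | Expected N at 0.30 |
|---|---|---|
| 2 | 2.76 | 20.20 |
| 2.5 | 3.45 | 20.65 |
| 3 | 4.14 | 21.10 |

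This is a rise of 10% to 15%. It assumes that the safety review and the IRB/FDA documentation take no time.

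**3. With review time.** Two weeks of review leaves a 4-week gap (0.92 month), or 1.8 to 2.8 patients. Four weeks leaves a 2-week gap (0.46 month), or 0.9 to 1.4. Six weeks closes the gap.

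**4. What is known at the earliest release.** Patient i starts at (i − 1)/r. Release is at 9/r + 1.38. Patient i has reached week 12 if i ≤ 10 − 1.38r, which gives 7, 6 or 5 of the 10 at 2, 2.5 or 3 per month. The rest have had their week-6 scan, and a progression there already counts as a failure. Under exponential progression-free survival with a 12-week rate of 0.30 (an assumption), the chance of progression by week 6 is 1 − √0.30 = 0.452. The mean number with known status is then:
- 2 per month: 7 + 3 × 0.452 = 8.4
- 2.5 per month: 6 + 4 × 0.452 = 7.8
- 3 per month: 5 + 5 × 0.452 = 7.3

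Suppose enrolment stopped as soon as 7 of 10 had visibly progressed. The plan does not state this, though it is natural in an open-label, single-centre study. A simulation of 400,000 trials then gives a mean of 0.54 to 1.11 gap patients per failing trial, and expected N of 18.8 to 19.1.

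**5. Single-histology branch.** With 5 patients per histology it needs at least 4 successes in one and none in the other. If both true rates are 30%: 2 × 0.03078 × 0.16807 = 0.010. At an assumed split of 55% and 10%, which the documents do not give, it is 0.151.

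**6. Accrual time.** 34/2 = 17.0 months reproduces section 15.2. At 2 per month, first-to-last enrolment is 9/2 + hold + 23/2, and the cruder form is 34/2 + hold.
- 6-week hold: 17.4 to 18.4 months.
- Wait to week 12: 18.8 to 19.8 months.

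On the cruder form, 17 months absorbs the 6-week hold at 34/(17 − 1.38) = 2.18 per month or faster, and a full 12-week wait at 34/(17 − 2.76) = 2.39 or faster.

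**7. Reading the two sections together.** Section 4.2 says accrual may not go on until a condition is met. That is a floor, and it does not promise that accrual restarts once the floor is reached. Section 15.1 supplies the other condition. Stage 1 is 10 patients, so leaving replacements aside the eleventh is a stage-2 patient, and stage 2 exists only if the count is at least 4. The histology rule also makes sense only if the count is known before stage-2 enrolment. Both conditions can hold at once, and the later one governs.

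**The case for a change.** The best case for a change is practical. Section 4.2 speaks of resuming accrual once the safety review is documented, a coordinator may work from that section alone, and one sentence would settle the matter at no cost to the design. In a failing trial, about 3 to 4 patients might otherwise receive an inactive drug before the failure is declared. The plan also does not say how such patients, or those in a histology that then closes, would be reported.

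Part of this stands: no sentence links the two sections, and at 2 per month the 17-month figure omits even the 6-week hold that the plan itself requires. The rest carries less weight. The exposure arises only if staff disregard the condition in section 15.1, and the 20.2 to 21.1 range also needs instant review and continued enrolment after visible failures. Sections 14.3 and 14.4 provide a check: stopping rules are among the statistical endpoints summarised for a monitoring committee that meets twice a month. The accrual estimate is weak evidence that no wait is intended, because it leaves out the explicit hold as well. Allowing a capped overlap between stages would be a different design choice, and nothing here shows it to be better.

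**Conclusion.** The plan can stand. Followed as written, stage-2 patients wait for both the safety review and the stage-1 count, and spelling this out would only record what section 15.1 already implies. If section 4.2 were misread as the sole gate, the worst case is about 2.8 to 4.1 early patients and an expected N of 20.2 to 21.1 against 18.4 at a 30% rate. That rests on even accrual at 2 to 3 per month and no review time. Six weeks of review removes the gap, and acting on visible progressions brings expected N to 18.8 to 19.1. Type I error, power, the 4/10 and 15/34 rules and the maximum of 34 do not move, provided the first 10 patients alone decide stage 1. The 17-month figure is optimistic by roughly 0.4 to 2.8 months at the slowest planned rate, depending on the hold and how the interval is counted, and is sound at about 2.4 per month or faster. It is a planning estimate and feeds no analysis.

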12.9 Stopping Rules

Adverse event stopping rule: Accrual will be temporarily suspended to this study if (a) at any time, 2 patients have experienced a grade 5 event considered at least possibly related to the study treatment and not related to disease progression or (b) more than 40% of all patients, when accrual is equal to or greater than 10 patients, have experienced a grade 3 or higher adverse event. In addition, each grade 5 event will be reviewed at the time of occurrence to determine whether study accrual should be suspended to protect the safety of patients. This adverse event stopping rule may be altered in the event of the study reopening after a temporary suspension or should new information become available related to the safety of the study drug.

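### Section 4.2 does not require enrolment among the first 10 patients to pause when a lead-in toxicity threshold is reached

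*Combined protocol and SAP*

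**What the plan says.** Section 4.2 justifies the lead-in by the limited clinical experience with ATX-101 and applies it to the first 10 patients. Four elements matter here.

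- **Review time:** "After 10 patients complete 2 cycles of treatment, the study investigators will review the safety data".
- **Accrual hold:** "The study will not proceed to further accrual until these 10 patients have completed two cycles or 6 weeks of study treatment". This governs accrual beyond the 10. No text staggers patients 1 to 10 or holds enrolment among them.
- **DLT threshold:** "If 3 or more patients in the safety lead-in population experience DLTs as defined below, the study team will consider terminating the study", or amending it to study another dose and schedule. For each patient, "this timeframe is the first two cycles of treatment".
- **Infusion-reaction threshold:** "if 2 or more events of grade 4 infusion related reaction occur, the study team will also consider terminating the study". No time is attached.

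Section 12.9 has a separate stopping rule. Part (a) suspends accrual at any time if two patients have a related grade 5 event. Part (b) concerns grade 3 or higher events in "more than 40% of all patients, when accrual is equal to or greater than 10 patients". Each grade 5 event is also reviewed when it occurs, to decide on suspension.

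Section 9.4.3 sends serious adverse events to the data and safety monitoring committee (DSMC) within 24 hours. Under 14.3 that committee meets twice a month, and under 14.4 it receives summaries of toxicities and stopping rules.

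**The concern.** A lead-in meant to limit exposure while little is known should say what happens if its own limit is reached partway through. Once a third patient has had a DLT, no later patient can bring the count back below three. As written, a site can follow 4.2 exactly and still start the remaining lead-in patients before the planned review. Those patients would begin a regimen that has already met the protocol's own criterion for considering termination or amendment.

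**Working it through.** **Which rules can act during patients 1 to 10**

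| Rule | Can it pause enrolment of patients 1 to 10 on DLT or grade 4 reaction counts? |
|---|---|
| 4.2 hold | No. It applies after patient 10. |
| 4.2 DLT threshold | The review is set for the end of the lead-in; no hold at crossing. |
| 4.2 grade 4 reaction threshold | Time not stated; no hold. |
| 12.9(a) and review of each grade 5 event | Grade 5 events only. |
| 12.9(b) | Starts at 10 accrued. More than 40% of 10 means at least 5 patients. |
| 9.4.3, 14.3, 14.4 | General oversight, not tied to either 4.2 count. A grade 3 DLT need not meet the serious-event definition in 9.2. |
| 8.2 | Governs the affected patient's own treatment only. |

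**Inputs.** From 4.2: 10 patients, a 6-week window and a threshold of 3. From 15.2: accrual of 2 to 3 per month. The stated accrual time reproduces: 34 / 2 = 17 months. The lead-in rule has no stated operating characteristics. The true DLT rate p is an assumption, shown from 10% to 50%.

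**Bounds.** At most 10 − 3 = 7 patients can start after the third DLT. Section 8.2 ends treatment after a grade 4 infusion reaction, so two such events need two patients, and at most 10 − 2 = 8 can start afterwards.

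**Illustration of the bound.** With even spacing at 2 per month, starts are about 15.2 days apart. Patient 10 starts near day 9 × 15.2 = 137, and the review falls no earlier than day 137 + 42 = 179. If patients 1 to 3 each have a DLT at the first infusion, the threshold is crossed near day 30. Seven more patients then start, and the review is about 149 days later. At 3 per month the crossing is near day 20 and the review about 113 days later.

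**Chance of reaching the threshold.** P(X ≥ 3) = 1 − Σ C(10,k) p^k (1−p)^(10−k), summed over k = 0, 1, 2. At p = 0.30 this is 1 − (0.028 + 0.121 + 0.233) ≈ 0.62.

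**Starts after crossing.** Lead-ins were simulated with Poisson accrual and DLT onset uniform over 6 weeks. Patients starting after the third DLT were counted. In each range the low end is 3 per month and the high end 2 per month.

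| Assumed DLT rate | Threshold reached | Mean later starts, given reached | At least one later start, given reached |
|---|---|---|---|
| 10% | 7% | 0.9–1.2 | 39–50% |
| 20% | 32% | 1.2–1.5 | 47–58% |
| 30% | 62% | 1.5–2.0 | 56–66% |
| 40% | 83% | 2.0–2.5 | 67–76% |
| 50% | 95% | 2.6–3.1 | 78–85% |

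Averaged over all lead-ins, including those that never cross, the mean is 0.06–0.09 later starts at 10% and 0.4–0.5 at 20%.

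**Sensitivity**

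- Evenly spaced starts with every DLT at the first infusion: about 3.0, 3.7 and 4.4 later starts at 30%, 40% and 50%, given crossing.
- A 14-day lag before every DLT is confirmed, which is an upper case: at 30%, 2.0 falls to 1.4 (2 per month) and 1.5 to 0.9 (3 per month).
- Two-event threshold, evenly spaced starts: mean later starts of 2.0–3.2 at an assumed 10% grade 4 reaction rate and 2.5–3.9 at 20%, from uniform to first-infusion onset.

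**The case against.** **The severe rates may be unlikely.** Section 3.2 reports no DLT and no related grade 3 or higher event in 21 patients. The one-sided 95% upper limit is 1 − 0.05^(1/21) ≈ 13% with all dose levels pooled. From the six patients at 60 mg/m² it is 1 − 0.05^(1/6) ≈ 39%, so 30% is not excluded at the study dose. This stands: the expected number of affected patients may be small, and a later start is not certain even after crossing. A reader might infer that patients will inevitably keep being started; the figures do not support that.

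**The wait to the review overstates the exposure.** At rates of 30% to 50%, the mean time from the third DLT to the planned review is about 7 to 12.5 weeks. Part of that falls after patient 10 has started, when accrual is already held and 12.9(b) applies. The window in which lead-in patients can still start averages about 2.2 to 6.8 weeks. This stands.

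**Later patients are not uninformative.** It is tempting to say that waiting adds nothing to the decision. Crossing is indeed fixed, but the team chooses between terminating and amending. The final count and the type and timing of events bear on that choice.

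**DLT status can lag onset.** Some definitions in 4.2 need more than 14 days, or 5 days, of persistence. This lowers the counts, though infusion reactions carry no such lag.

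**Other safeguards exist.** It would be wrong to say that only two deaths can prompt a pause, since every grade 5 event is reviewed. Investigators and the DSMC can also act at discretion. Nor does the text establish that the grade 4 count is read only at the end; its sentence can be taken to apply as events occur. On either reading, no enrolment hold is stated.

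**Conclusion.** The point holds as a gap in the rule and should be corrected. No provision makes enrolment among patients 1 to 10 pause at the third DLT, and the timing of the grade 4 reaction threshold is unstated. The documents do not contradict themselves here, and the thresholds themselves are not in question.

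The size is conditional. If the DLT threshold is reached, about one to three further patients start on average, and seven at most. Reaching it ranges from uncommon (7% at a 10% rate) to near certain (95% at 50%). These figures rest on assumed DLT rates, Poisson accrual at the planned pace, uniform onset and no confirmation lag.

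**What to change.** Leave both thresholds unchanged and add to 4.2:

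- DLTs and grade 4 infusion-related reactions in the lead-in are counted as events occur.
- If either threshold is reached, new enrolment pauses and the 4.2 review is held then.
- Enrolment up to 10 resumes only after that review is documented, in the way 4.2 already requires for the IRB and FDA.
- If neither threshold is reached, the end-of-lead-in review stays as planned.

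This concerns new enrolment only; patients already on treatment stay under the existing rules.

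The cost is a short text change and a possible earlier pause in a cohort that also supplies stage 1 of the Simon design (15.1) and the paired biopsies (13.1). The pause arises only in lead-ins that reach a threshold. For the DLT rule that is about a third of them at an assumed 20% rate. The decision would then rest on fewer patients.
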